APPENDIX E. MANAGEMENT OF POTENTIAL HY'S LAW CASES

INTRODUCTION

During the course of the study, the investigator will remain vigilant for increases in liver biochemistry. The investigator is responsible for determining whether a participant meets PHL criteria at any point during the study.

The investigator participates, in conjunction with Incyte clinical project and pharmacovigilance representatives, in the review and assessment of cases fulfilling PHL criteria to ascertain whether there is an alternative explanation for the elevations in liver biochemistry other than drug-induced liver injury caused by the study drug.

The investigator fulfills requirements for the recording of data pertaining to PHL or Hy's law cases and AE/SAE reporting according to the outcome of the review and assessment in line with standard safety reporting processes.

DEFINITIONS

For the purpose of this process, definitions are as follows:

Potential Hy's Law

An increase in AST or ALT > $3 \times$ ULN and total bilirubin > $2 \times$ ULN at any point during the study. The elevations do not have to be at the same time or within a specified timeframe.

Hy's Law

An increase in AST or $ALT \ge 3 \times ULN$ and total bilirubin $> 2 \times ULN$, where no other reason can be found to explain the combination of increases (eg, elevated serum ALP indicating cholestasis, viral hepatitis, another drug).

ACTIONS REQUIRED IN CASES OF AST OR ALT > 3 × ULN OR TOTAL BILIRUBIN $\ge 2 \times ULN$

Identification and Determination of Potential Hy's Law

To identify cases of AST or $ALT > 3 \times ULN$ or total bilirubin $> 2 \times ULN$ and consequently determine whether the participant meets PHL criteria, please follow the instructions below:

- Review the laboratory report and if a participant has AST or ALT > 3 × ULN OR total bilirubin > 2 × ULN at any visit:
 - Determine without delay whether the participant meets PHL criteria by reviewing laboratory reports from all previous visits.
 - Enter the laboratory data into the laboratory eCRF as soon as possible.

Potential Hy's Law Criteria Not Met

If the participant has NOT had AST or $ALT \ge 3 \times ULN$ AND total bilirubin $> 2 \times ULN$ at any point in the study (the elevations do not have to be at the same time or within a specified timeframe), irrespective of ALP, please follow the instruction below:

• Perform follow-up on subsequent laboratory results according to the guidance provided in Section 6.5.

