Potential Hy's Law Criteria Met

If the participant has had AST or $ALT \ge 3 \times ULN$ AND total bilirubin $> 2 \times ULN$ at any point in the study (the elevations do not have to be at the same time or within a specified timeframe), irrespective of ALP, please follow the instruction below:

- Have the participant interrupt study drug.
- Notify the Incyte study team without delay.
 - The investigator, or designee, should contact the medical monitor to discuss and agree upon an approach for the study participant's follow-up and the continuous review of data.
- Monitor the participant until liver biochemistry parameters and appropriate clinical symptoms and signs return to normal or baseline levels, or as medically indicated.
- Investigate the etiology of the event and perform any relevant diagnostic investigations as discussed with the medical monitor.
- Enter the laboratory data into the laboratory CRF as soon as possible.
- If at any time (in consultation with the medical monitor) the PHL case meets serious criteria, report it as an SAE using standard reporting procedures.

REVIEW AND ASSESSMENT

No later than 3 weeks after the biochemistry abnormality is initially detected and the criteria for PHL are met, the medical monitor, Incyte pharmacovigilance physician, and investigator will discuss and review available data and agree on whether there is an alternative explanation for the elevations in liver biochemistry other than drug-induced liver injury caused by the study drug. Participant matter experts will be included in the review as appropriate.

Evaluation of Alternative Causes

In order to gather additional clinical information to seek other possible causes of the observed liver test abnormalities, the following alternative etiologies should be considered, including but not limited to:

- Active viral hepatitis
- Alcoholic and autoimmune hepatitis

- Hepatobiliary disorders
 - Biliary tract disease, such as migration of gallstones or intrahepatic lesions, more often causes cholestatic injury initially and should be investigated with gallbladder and ductal imaging studies, especially if ALP is increased. Malignant interruption of the biliary tract also should be considered.
- Concomitant treatment
- Other causes such as systemic infections (eg, bacterial, fungal, viral), nonalcoholic steatohepatitis, and cardiovascular diseases

Actions After Review and Assessment

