According to outcome of the review and assessment, please follow the instructions below:

If there **is** an agreed alternative explanation for the AST or ALT **and** total bilirubin elevations, a determination of whether the alternative explanation is an AE will be made and subsequently whether the AE meets the criteria for an SAE.

- If the alternative explanation is not an AE, record the alternative explanation on the appropriate CRF if possible.
- If the alternative explanation is an AE/SAE, record the AE/SAE in the eCRF accordingly and follow the standard study processes.
- Have the participant resume study drug as per Protocol guidelines.

If it is agreed that there is no explanation that would explain the AST or ALT and total bilirubin elevations:

- Have the participant permanently discontinue study drug and perform end-of-treatment procedures.
- Report an SAE (report term "Hy's Law").
 - The 'medically important' serious criterion should be used if no other serious criteria apply.
 - As there is no alternative explanation for the Hy's law case, a causality assessment of related should be assigned.
- If there is an unavoidable delay of over 3 weeks in obtaining the information necessary to assess whether or not the case meets the criteria for a Hy's law case, then it is assumed that there is no alternative explanation until such time as an informed decision can be made. Report an SAE (report term "Potential Hy's Law") applying serious criteria and causality assessment as per above.

ACTIONS REQUIRED FOR REPEAT EPISODES OF AST OR ALT > 3 × ULN AND/OR TOTAL BILIRUBIN > 2 × ULN

The requirement to conduct follow-up, review, and assessment of a repeat occurrence(s) of PHL is based on the nature of the alternative cause identified for the previous occurrence.

If the alternative cause for the previous occurrence of PHL was not chronic or progressing malignant disease, please follow the process for PHL review and assessment as described in this appendix.

If the alternative cause for the previous occurrence of PHL was chronic or progressing malignant disease, please follow the instructions below:

- Determine whether there has been a significant change* in the participant's condition.
 - If there is no significant change, no action is required.
 - If there is a significant change, follow the process described for PHL review and assessment as described in this appendix.

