9.3.4. Potential Drug-Induced Liver Injury Events

According to FDA's guidance on Drug-Induced Liver Injury (2009), the criteria for potential DILI events include the following:

- ALT \geq 3 × ULN
- ALT \geq 5 × ULN
- ALT $\geq 10 \times ULN$
- ALT $\geq 20 \times ULN$
- AST \geq 3 × ULN
- AST \geq 5 × ULN
- AST $\geq 10 \times ULN$
- AST $\geq 20 \times ULN$
- ALT or AST \geq 3 × ULN
- ALT or AST \geq 5 × ULN
- ALT or AST $\geq 10 \times ULN$
- ALT or AST $\geq 20 \times ULN$
- Alkaline phosphatase $\geq 1.5 \times ULN$
- Total bilirubin $\geq 2 \times ULN$
- ALT and/or AST \ge 3 × ULN and total bilirubin \ge 2 × ULN

Note that combination of values need to be measured on the same day.

The number and percentage of participants with postbaseline liver specific function test values that meet these criteria will be presented at each scheduled visit by treatment group. Participants with potential DILI events will also be listed.

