3.3.4.3	Summary of Potential Clinically Important Laboratory Values by Visit for Participants Who Took Only Povorcitinib 45 mg or 75 mg During Overall Period	Safety	
3.3.5.x	Summary of Potential Drug Induced Liver Injury Events by Visit in the PC Period	Safety/Ext-Ev	

Table No.	Title	Population	Standard
3.3.5.3	Summary of Potential Drug Induced Liver Injury Events by Visit for Participants Who Took Only Povorcitinib 45 mg or 75 mg During Overall Period	Safety	
3.4 Vital Sig	gns		
3.4.1.x	Summary of Systolic Blood Pressure in the PC Period	Safety/Ext-Ev	Х
3.4.1.3	Summary of Systolic Blood Pressure for Participants Who Took Only Povorcitinib 45 mg or 75 mg During Overall Period	Safety	Х
3.4.2.x	Summary of Diastolic Blood Pressure in the PC Period	Safety/Ext-Ev	Х
3.4.2.3	Summary of Diastolic Blood Pressure for Participants Who Took Only Povorcitinib 45 mg or 75 mg During Overall Period	Safety	Х
3.4.3.x	Summary of Pulse in the PC Period	Safety/Ext-Ev	Х
3.4.3.3	Summary of Pulse for Participants Who Took Only Povorcitinib 45 mg or 75 mg During Overall Period	Safety	Х
3.4.4.x	Summary of Respiratory Rate in the PC Period	Safety/Ext-Ev	Х
3.4.4.3	Summary of Respiratory for Participants Who Took Only Povorcitinib 45 mg or 75 mg During Overall Period	Safety	Х
3.4.5.x	Summary of Body Temperature in the PC Period	Safety/Ext-Ev	Х
3.4.5.3	Summary of Body Temperature for Participants Who Took Only Povorcitinib 45 mg or 75 mg During Overall Period	Safety	Х
3.5 ECG		•	
3.5.1.1.x	Summary of PR Interval (ms) From 12-Lead ECG by Visit in the PC Period	Safety/Ext-Ev	Х
3.5.1.2.x	Summary of QRS Interval (ms) From 12-Lead ECG by Visit in the PC Period	Safety/Ext-Ev	Х
3.5.1.3.x	Summary of QT Interval (ms) From 12-Lead ECG by Visit in the PC Period	Safety/Ext-Ev	Х
3.5.1.4.x	Summary of QTcF Interval (ms) From 12-Lead ECG by Visit in the PC Period	Safety/Ext-Ev	Х
3.5.1.5.x	Summary of Heart Rate (bpm) From 12-Lead ECG by Visit in the PC Period	Safety/Ext-Ev	Х
3.5.1.6.x	Summary of Outliers of QT and QTcF Interval Values (ms) From 12-Lead ECG by Visit in the PC Period	Safety/Ext-Ev	Х
3.5.1.7.x	Summary of Clinically Significant ECG Abnormality by Visit in the PC Period	Safety/Ext-Ev	Х

Figures

Figure No.	Title	Population
4.1 Primar	y Efficacy	
4.1.1	Proportion of Participants Achieving \geq 4-Point Improvement in Itch NRS Score by Visit in the PC Period Using Nonresponder Imputation	ITT

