2.6 Efficacy		
2.6.1.x	Itch NRS Score and \geq 4-Point Improvement Responses in the PC Period	
2.6.2.x	IGA Score and IGA-TS Responses in the PC Period	
2.6.3.x	Itch NRS and IGA Score in the PC Period	
2.7 Adverse	Events	
2.7.1.	Adverse Events	
2.7.2.x	Serious Adverse Events in the PC Period	
2.7.3.x	Grade 3 and Higher Adverse Events in the PC Period	
2.7.4.x	Fatal Adverse Events in the PC Period	
2.7.5.x	Treatment-Related Adverse Events in the PC Period	
2.7.6.x	Adverse Events Leading to Dose Interruption in the PC Period	
2.7.7.x	Adverse Events Leading to Discontinuation of Study Drug in the PC Period	
2.8 Laborat	ory Data	
2.7.8.x	Adverse Events Requiring Concomitant Medications in the PC Period	
2.8.1.1.x	Clinical Laboratory Values in the PC Period - Hematology	
2.8.1.2.x	Clinical Laboratory Values in the PC Period - Chemistry	
2.8.1.3.x	Clinical Laboratory Values in the PC Period - Lipid Panel	
2.8.1.4.x	Clinical Laboratory Values in the PC Period - Urinalysis	
2.8.1.5.x	Clinical Laboratory Values in the PC Period - Thyroid Function Markers and Inflammation Marker	
2.8.2.1.x	Abnormal Clinical Laboratory Values in the PC Period - Hematology	
2.8.2.2.x	Abnormal Clinical Laboratory Values in the PC Period - Chemistry	
2.8.2.3.x	Abnormal Clinical Laboratory Values in the PC Period - Lipid Panel	
2.8.2.4.x	Abnormal Clinical Laboratory Values in the PC Period - Thyroid Function Markers and Inflammation Marker	
2.8.3.x	Potentially Clinically Important Laboratory Values in the PC Period	
2.8.4.x	Potential Drug Induced Liver Injury Events in the PC Period	
2.9 Vital Sig	gns	
2.9.1.x	Vital Signs in the PC Period	

Listing No.	Title
2.9.2.x	Abnormal Vital Sign Values in the PC Period
2.9.3.x	Alert Vital Sign Values in the PC Period

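### SAP 9.3.4 counts combined ALT/AST and bilirubin elevation only on the same day and by scheduled visit, so no listed laboratory table gives a linked per-participant count by arm of the any-time cases in protocol Appendix E (low impact, optional)

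*SAP*

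**What the plan says.** SAP 9.3.4 lists criteria for potential drug-induced liver injury. Most concern one analyte, or ALT or AST at rising multiples of ULN. One is combined: ALT and/or AST at or above 3 × ULN together with total bilirubin at or above 2 × ULN. The section adds: "Note that combination of values need to be measured on the same day". Counts and percentages "will be presented at each scheduled visit by treatment group", and "Participants with potential DILI events will also be listed".

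SAP Appendix A carries this through. Table 3.3.5.x is titled "Summary of Potential Drug Induced Liver Injury Events by Visit in the PC Period". Table 3.3.5.3 is the by-visit equivalent for participants who took only 45 mg or only 75 mg. Listing 2.8.4.x is "Potential Drug Induced Liver Injury Events in the PC Period".

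Protocol Appendix E defines potential Hy's law by the same pair of analytes at any point in the study: "The elevations do not have to be at the same time or within a specified timeframe". The instructions for when the criteria are met repeat that "the elevations do not have to be at the same time or within a specified timeframe". Meeting them triggers interruption of study drug, notification of the sponsor's team, and a joint review within 3 weeks. If no alternative explanation is agreed, or the information is still outstanding after 3 weeks, the instruction begins "Report an SAE (report term", with a Hy's law or potential Hy's law term.

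**The concern.** The trial manages participants under an any-time rule, but its only combined laboratory summary uses a same-day rule. Someone with raised ALT at one visit and raised bilirubin at the next meets the protocol's definition yet cannot be counted in the SAP's combined row. Someone whose coincident elevations are seen only at an unscheduled repeat (protocol 8.7) may also be missed, because the table is laid out by scheduled visit.

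At stake is a descriptive safety figure: how many participants in each arm had both elevations. By-visit cells do not give it, because they count visits rather than people and cannot be added up.

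**Working it through.** There is no figure in the plan to reproduce; the check compares definitions.

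**Step 1. The two rules side by side**

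| | SAP 9.3.4 combined row | Protocol Appendix E |
|---|---|---|
| Timing | Both values on one day | Any time in the study |
| Unit shown | Participants at each scheduled visit | The participant |
| Thresholds | ≥ 3 × ULN and ≥ 2 × ULN | > 3 × ULN and > 2 × ULN in the definition; ≥ 3 × ULN for ALT/AST in later instructions |

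The mixed signs within Appendix E may come from text extraction. Nothing below depends on them.

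**Step 2. Do the rules count differently?** Take four invented participants, with ALT 4 × ULN and bilirubin 2.5 × ULN when raised:

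- A: both at Week 4.
- B: ALT at Week 4, bilirubin at Week 6.
- C: both at Week 4 and again at Week 6.
- D: both on one day, at an unscheduled visit between Weeks 4 and 6.

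If unscheduled values stay out of the by-visit table, the combined row shows 2 at Week 4 (A, C) and 1 at Week 6 (C). The cells add to 2 + 1 = 3 but come from 2 people. The any-time rule counts 4. B is excluded by the same-day condition and D by the scheduled-visit layout.

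**Step 3. Could the other laboratory tables supply the linked count?** The shift tables to worst value and worst CTCAE grade (SAP 9.3.2; Tables 3.3.2.2.x and 3.3.3.2.x) summarise each participant over the period, but one test at a time. Compare two invented arms of 35, all other values normal:

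- Arm A: one participant has ALT 4 × ULN with bilirubin 1.5 × ULN at Week 8, then ALT 2.5 × ULN with bilirubin 2.2 × ULN at Week 12.
- Arm B: one participant has those ALT values, and a different participant has those bilirubin values.

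| Output | Arm A | Arm B |
|---|---|---|
| ALT ≥ 3 × ULN | 1 at Week 8 | 1 at Week 8 |
| Bilirubin ≥ 2 × ULN | 1 at Week 12 | 1 at Week 12 |
| Same-day combined row, all 6 scheduled placebo-controlled visits (Weeks 2, 4, 6, 8, 12, 16) | 0 | 0 |
| Worst value, by test | ALT 4, bilirubin 2.2 (× ULN) | ALT 4, bilirubin 2.2 (× ULN) |
| Both elevations in one person, any day | 1 of 35 | 0 of 35 |

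The planned laboratory tables are the same for the two arms; only the linked count separates them.

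**Step 4. Where do such cases appear?**

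- Single-analyte rows of Table 3.3.5.x, for scheduled-visit values.
- Per-test shift tables.
- Listing 2.8.4.x, since each single-analyte threshold is itself a listed criterion.
- Serious TEAE tables, if unexplained or unresolved after 3 weeks.
- Probably the TEAE and dose-interruption tables (SAP 9.2.2; Tables 3.2.2.x and 3.2.15.x). Appendix E requires interruption, and protocol 9.1 makes a laboratory abnormality that needs a change in study drug an AE. This applies to recognised cases in participants still on drug.

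None of the laboratory or AE tables shows the linked pair. The listing does, but gives no count by arm.

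**The case against.** The strongest reply is that nothing here is inconsistent. Appendix E is a trigger for case management, deliberately broad. SAP 9.3.4 is a descriptive summary that does not claim to count potential Hy's law, and a same-day rule is a legitimate, more specific choice. Protocol 10.4.3 promises summary statistics, incidence of abnormal values and shift tables, which the SAP supplies, and it plans no formal comparison of laboratory data between groups. With 35 per arm, and with viral hepatitis and cholestatic liver disease among the exclusions, any cases may be few enough to read from the listing. The shells for Tables 3.3.5.x sit in a separate document, so an any-time row may already exist.

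Most of this stands, and it sets the weight of the point. A reader might go further and infer that the SAP contradicts the protocol, or that potential Hy's law cases would go unmanaged or disappear from the report. The documents do not support either reading. Case identification, interruption and SAE reporting run under Appendix E whatever the SAP tabulates, and the cases reach the outputs listed in Step 4.

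What survives is narrower. The SAP states a rule that shuts out of its only combined row some cases that the protocol itself defines, and no other listed table restores the link. For non-serious cases with an agreed alternative explanation, the AE tables would probably show an interruption but not the pair. Their count by arm would have to be rebuilt from the listing.

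**Conclusion.** The point holds as a low-impact, optional improvement to safety reporting. The same-day, by-visit rule cannot count non-coincident elevations, and no listed laboratory table gives a linked per-participant count by arm. Efficacy, type I error and participant management are unaffected.

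The size cannot be stated: the documents give no rate for these elevations, and the number of participants affected may be zero. The illustrations show only that the rules can differ, not how often they will.

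The conclusion rests on the SAP text and the table titles. If the Table 3.3.5.x shell already contains an any-time row, the point falls away. The statement that recognised cases probably reach the AE and dose-interruption tables rests on reading Appendix E together with protocol 9.1; neither document says so outright.

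**What to change.** First check the Table 3.3.5.x shell. If it has no such row, keep the same-day by-visit row and add to SAP 9.3.4, for Tables 3.3.5.x and 3.3.5.3:

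- One row per treatment group with the number (%) of participants whose highest postbaseline ALT or AST and highest postbaseline total bilirubin within the period both meet the SAP thresholds, regardless of day, using scheduled and unscheduled values, each participant counted once.
- A flag in Listing 2.8.4.x for pairs that cross from the placebo-controlled to the extension period, without attributing them to an extension treatment group.

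The row will not equal the full set of Appendix E cases. Cross-period pairs stay in the listing, except that Table 3.3.5.3 can count them for participants who took only 45 mg or only 75 mg, because its period is the whole study. Pairs that rely on a value before the first dose also fall outside a postbaseline row. A footnote should say so.

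The strict and non-strict inequality signs in SAP 9.3.4 and protocol Appendix E, and within Appendix E, should also be reconciled, so that table and protocol definition agree at the boundary values.

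The cost is a short SAP addition, one row in existing tables and one listing flag, from data already collected. The downside is that a less specific count will stand beside the same-day one and needs a clear label.

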9.4. Vital Signs

Values at each scheduled visit, change, and percentage change from baseline for vital signs, including systolic blood pressure, diastolic blood pressure, pulse, temperature, respiratory rate, and weight will be summarized descriptively. Baseline will be determined according to Section 4.1.3.

Normal ranges for vital sign values are defined in Table 7. For participants exhibiting vital sign abnormalities, the abnormal values will be listed along with their assigned treatment group. Alert vital signs are defined as an absolute value outside the defined normal range and percentage change greater than 25%. Note that the definition of alert vital signs does not apply for body temperature and weight. The abnormal values for participants exhibiting alert vital sign abnormalities will be listed.

Parameter	High Threshold	Low Threshold
Systolic blood pressure	\leq 155 mmHg	\geq 85 mmHg
Diastolic blood pressure	$\leq 100 \text{ mmHg}$	\geq 40 mmHg
Pulse	$\leq 100 \text{ bpm}$	\geq 45 bpm
Temperature	≤ 38°C	≥ 35.5°C
Respiratory rate	\leq 24 breaths/min	\geq 8 breaths/min

Table 7:Normal Ranges for Vital Sign Values

9.5. Electrocardiograms

Twelve-lead ECGs, including PR, QT, QRS and QTcF intervals, will be obtained for each participant during the study. Values at each scheduled visit, change, and percentage change from baseline will be summarized for each ECG parameter. Baseline will be determined as the average of all nonmissing values before the first administration of povorcitinib or placebo.

Normal ranges for ECG values are defined in Table 8. The ECG values will also be considered abnormal if the absolute percentage change from baseline is more than 25% (30% for QRS interval). Participants exhibiting ECG abnormalities will be listed with study visit and assigned treatment group. Abnormal values for participants with alert ECG values, defined as both the absolute value and the percentage change from baseline being outside normal ranges, will be identified and listed. Outliers of QT and QTcF values, defined as absolute values > 450 millisecond, > 500 millisecond, or change from baseline > 30 millisecond, will be summarized.

Table 8:	Normal Ranges for Electrocardiogram Intervals	
----------	---	--

Parameter	High Threshold	Low Threshold
PR	\leq 220 ms	≥ 75 ms
QT	$\leq 500 \text{ ms}$	≥ 300 ms
QRS	$\leq 120 \text{ ms}$	≥ 50 ms
QTcF	\leq 450 ms	≥ 295 ms

10. INTERIM ANALYSES

There are no planned, formal interim analyses for this study.

